- mothers with history of bleeding disorders or taking any other medication that may increase the risk of bleeding
- infants with bleeding disorders or receiving any other medication that may increase the risk of bleeding

Study Procedures:

Maternal Dietary intake and breastmilk samples will be collected and assessed at initiation of supplementation and at weeks 2, 4, and 8. Maternal breast expression and breastfeeding patterns; anthropometry (weight, height, circumferences); exercise patterns; and smoking habits will be obtained at week 4.

Maternal blood and buccal swabs (saliva) will be collected and assessed at baseline and at weeks 4, and 8.

Infant Dietary intake, blood samplesbuccal swabs (saliva), and stool samples will be collected and assessed at baseline and at weeks 2, 4, and 8. – see Figure 3.

Maternal blood collected will be 5 mL at each collection therefore a total of 15 mL whole blood collected for the study. Infant blood collected will be \sim 1 mL at each collection therefore a total of \sim 5 mL whole blood collected. The infant blood will be collected during routine nutritional lab collections which are clustered with standard of care.

The dietary and supplemental intake of the mother will be assessed at The Bionutrition Center using NDSR software and the dietary intake of the infant will be calculated by the Neonatal Dietitian. The fatty acid contents of the breastmilk, blood, and stool samples will be measured by gas chromatography in our laboratory_using Bligh-Dyer extraction (Chloroform: Methanol (2:1))[34]. Cytokine (IL-10, IL 6, IL-8, IL 1B, TNF a, TGF, adiponectin, leptin) and sRAGE concentrations will be examined in maternal milk, and maternal and infant blood samples using a MSD SECTOR® Imager 2400A. This instrument allows for the analyses of 40 individual samples in duplicate at one time using a 96-well format. Infant growth, clinical outcome, and development data will be collected. Breastmilk samples will be analyzed for fatty acids and certain proteins as is routinely analyzed at Human milk banks of North America and clinically at Cincinnati Children's Hospital Medical Center. Cytokine analysis will be performed on infant stool samples. Saliva samples will be analyzed for genetic polymorphisms. Buccal swabs (saliva) will be analyzed for fatty acids.

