Statistical Plan: All data analyses will employ intention to treat principles. In our primary analysis, ANOVA will be used to compare DHA levels at four weeks in the breast milk of mothers assigned to the different concentrations of DHA supplements. As in any prospective study, If we experience substantial loss to follow-up (e.g., > 10% of subjects), we will fit a linear mixed model [35] We will use two sample t tests to compare infant blood DHA concentrations and TNF-alpha and IL-10 levels at 8 weeks of infants randomized to DHA-supplemented milk. The comparison of DHA concentrations will be performed at a significance level of 0.05 while the comparison of TNF-alpha and IL-10 levels will be performed at a significance level of 0.025 to adjust for the two outcomes. All analyses will be performed using SAS (SAS Inc., Cary, NC). Our sample size determination to detect a two-fold difference in the DHA levels at four weeks in expressed milk of mothers assigned DHA treatments, we will need data on a total of 16 mothers at week 4 (8 per group). This sample size calculation was based on 90% power, a two-sided significance level of 0.025, and a coefficient of variation (CV) of 30%; the CV is based on a previous study [36]. Assuming a conservative 20% loss to follow-up before week 4, we will enroll enough mother-infant pairs to achieve our desired sample size of 16 at 4 weeks. It is expected that evaluable data at week 4 from at least sixteen of the mother/baby pairs (8 pairs per group) will be obtained. The University Hospital Investigational Pharmacy will randomize participants per the Consolidated Standards of Reporting Trials (CONSORT) framework. Secondary outcomes will use linear mixed models and Bonferroni correction.

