Maternal blood – fatty acids Diet analysis Buccal swabs (saliva) Infant blood - fatty acids, cytokines, and sRAGE Nutrition labs Growth measures: Weight, length, head circumference Diet analysis Stool from diaper Buccal swabs (saliva)	Infant blood - fatty acids and cytokines labs, sRAGE Stool from diaper Buccal swabs (saliva) Growth measures	Maternal blood – fatty acids Diet analysis Exercise and Smoking habits Breast milk expression and breastfeeding patterns and concerns Anthropometry (weight, height and circumferences) Buccal swabs (saliva) Infant blood fatty acids and cytokines labs, sRAGE Stool from diaper Buccal swabs (saliva) Growth measures	Buccal swabs (saliva) Infant blood - fatty acids and cytokines labs, sRAGE Buccal swabs (saliva) Stool from diaper Growth measures Body composition using the Pea Pod ® air displacement isolette

Figure 3. Study	time table for r	recruitment, samp	ole, and data collection

Summary and Significance:

Premature birth is responsible for 75% of perinatal death [37]. Inflammatory conditions such as necrotizing enterocolitis (NEC), bronchopulmonary dysplasia (BPD), and retinopathy of prematurity (ROP) in the preterm infant are a tremendous source of morbidity and mortality. DHA is a key regulator of inflammation. Breast milk is the ideal delivery vehicle for DHA based upon the ability of the breast to provide balanced fatty acid composition as well as anti-infective molecules. Further understanding of the mechanisms could ensure our nutritional strategy is optimal.

References:

- 1. Fanaroff, A.A., et al., *Trends in neonatal morbidity and mortality for very low birthweight infants*. Am J Obstet Gynecol, 2007. **196**(2): p. 147 e1-8.
- Innis, S.M., Essential Fatty Acid Transfer & Fetal Development. Placenta, 2005. Suppl A: p. S70-75.
- 3. Turner, N., P.L. Else, and A.J. Hulbert, *Docosahexaenoic acid (DHA) content of membranes determines molecular activity of the sodium pump: implications for disease states and metabolism.* Naturwissenschaften, 2003. **90**(11): p. 521-3.
- 4. SanGiovanni, J.P., et al., *Meta-analysis of dietary essential fatty acids and long-chain polyunsaturated fatty acids as they relate to visual resolution acuity in healthy preterm infants.* Pediatrics, 2000. **105**(6): p. 1292-8.
- 5. Innis, S.M., *Perinatal biochemistry and physiology of long-chain polyunsaturated fatty acids*. J Pediatr, 2003. **143**(4 Suppl): p. S1-8.

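### The Statistical Plan gives the three infant blood outcomes competing analyses (week-8 t tests or linear mixed models) without saying which applies, and the t tests leave the earlier infant samples unused

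*Combined protocol and SAP*

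**What the plan says.** All of the analysis text is in the Statistical Plan. The primary analysis is an ANOVA of milk DHA at week 4. Three later statements bear on the infant outcomes:

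- A fallback, placed between the milk ANOVA and the infant tests and naming no outcome: "If we experience substantial loss to follow-up (e.g., > 10% of subjects), we will fit a linear mixed model".
- The infant tests: "We will use two sample t tests to compare infant blood DHA concentrations and TNF-alpha and IL-10 levels at 8 weeks". DHA is tested at 0.05, and "the comparison of TNF-alpha and IL-10 levels will be performed at a significance level of 0.025 to adjust for the two outcomes".
- The closing sentence of the section: "Secondary outcomes will use linear mixed models and Bonferroni correction".

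The section opens with "All data analyses will employ intention to treat principles". Its sample-size text covers week-4 milk only and includes an allowance: "Assuming a conservative 20% loss to follow-up before week 4".

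Under Study Procedures, the sentence that lists infant blood among the infant samples ends "stool samples will be collected and assessed at baseline and at weeks 2, 4, and 8". Figure 3 shows infant fatty acids and cytokines at all four visits and labels the last one as week 8 or discharge. Study Design limits infant sampling to the NICU stay. No section says how an infant death before week 8 enters the analysis.

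**The concern.** A two-sample t test at week 8 needs a week-8 value. An infant without one contributes nothing to it, even if samples from baseline and weeks 2 and 4 were assayed. In a trial of about 20 pairs that gives up information already paid for.

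The method is also not fixed. The infant tests are written without condition, the sentence before them switches to a mixed model once loss is substantial, and the last sentence of the section assigns mixed models to secondary outcomes. Milk DHA at week 4 is the only analysis called primary, so the infant outcomes may well be secondary. An analyst could defend either method, and could choose after seeing the losses and the results. The significance levels have the same problem: 0.05 and 0.025 are stated, yet a general Bonferroni rule follows.

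These are the only named tests of infant DHA and infant cytokines, so they carry the infant part of Aims 1 and 2.

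**Working it through.** **1. The plan's own sample size.** Inputs from the Statistical Plan: two-fold difference, CV 30%, 90% power, two-sided 0.025. Take means of 1 and 2, so the SDs are 0.3 and 0.6.
- Root-mean-square SD = √((0.09 + 0.36)/2) = 0.474, so d = 1/0.474 = 2.108.
- The noncentral t calculation gives 8 per group (power 94.3%), which reproduces the stated 16.
- With the 20% allowance, enrolment is 16/0.80 = 20 pairs. This is derived; the plan does not state it.

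**2. How often the fallback would be triggered.** More than 10% of 20 means 3 or more lost. Assume independent losses at a true rate of 20%:
- P(0, 1 or 2 lost) = 0.0115 + 0.0576 + 0.1369 = 0.206.
- P(3 or more lost) = 1 − 0.206 = 0.794, about 79%.

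If the fallback covers the infant outcomes, the mixed model would be used about four times in five and the t test about one time in five.

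**3. What the week-8 t test can detect.** Solve for d at 80% power with degrees of freedom 2n − 2 and noncentrality d√(n/2), two-sided (the plan does not state sidedness for these tests). No week-8 loss rate is given, so the rows are assumptions. The 36% row continues the 20% rate for a second period: 1 − 0.8² = 0.36.

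| Loss by week 8 | Infants per arm | At 0.05 (DHA) | At 0.025 (cytokines) | Standard error, √(2/n) |
|---|---|---|---|---|
| 20% | 8 | 1.51 SD | 1.70 SD | 0.50 SD |
| 36% | 6.4 | 1.72 SD | 1.96 SD | 0.56 SD |
| 40% | 6 | 1.80 SD | 2.04 SD | 0.58 SD |

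**4. Precision of the two methods.** Simulation with 20 infants, a true 1 SD reduction, exchangeable correlation 0.5 or 0.7, and two loss steps of about 20% each (log-odds slope 1 on the last observed value), about 400 runs per setting:

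| | Week-8 t test | Random-intercept mixed model |
|---|---|---|
| Mean estimated reduction | 0.92 and 0.91 SD | 0.98 and 1.01 SD |
| SD of the estimate | 0.52 and 0.48 | 0.45 and 0.35 |
| Power at 0.025 | 24% and 24% | 40% and 66% |

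Type I error was near 0.025 for each method. A second simulation (20 infants, 1 SD effect) gave SDs of 0.55 and 0.51 for the t test against 0.48 and 0.36 for the mixed model. Part of the gain comes from using baseline. The simulated correlation also matches the fitted model, which favours it.

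**5. Possible bias from loss.** All inputs here are assumed.
- With log-odds slope 1 or 2, the week-8 completer difference was 0.84 to 0.93 SD for a true 1 SD. That is a shift of 0.07 to 0.16 SD towards the null.
- If lost infants average 1 SD worse than those retained, the shift is the difference in loss rates times 1 SD. For 10% against 30% it is (0.30 − 0.10) × 1 = 0.2 SD; for equal rates it is 0.
- Extreme bound, with the highest values always lost: the mean falls by φ(z)/(1 − p), which is 0.350 SD at 20% loss and 0.644 SD at 40%. The difference, 0.644 − 0.350 = 0.294 SD, is about half a standard error.

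**6. Significance levels.** 0.025 is 0.05/2 for the two cytokines. Bonferroni over all three infant outcomes would give 0.05/3 = 0.0167. The plan does not say which rule governs.

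**The case against.** The best defence is that the plan already provides mixed models. The fallback names no outcome, so nothing in the text confines it to milk, and the closing sentence on secondary outcomes can be read to cover the infant tests. On either reading, infants with earlier samples contribute. That stands against any claim that the plan definitely discards those samples. It does not remove the ambiguity, because the t tests are stated without condition and no sentence sets the order of precedence.

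A reader might infer something stronger: that infants who die or leave before week 8 cannot be analysed, that at least 20% will be missing, and that the survivor comparison is therefore biased. The documents do not support this:
- The 20% is described as conservative and covers loss of pairs before week 4. It is neither a death rate nor a floor for week-8 loss, and it would include maternal reasons.
- Infants discharged early may have a final sample under the last column of Figure 3.
- Summary and Significance says that inflammatory conditions in preterm infants "are a tremendous source of morbidity and mortality", but this is general background without a rate.
- Bias between arms needs loss, or its link to the outcome, to differ by arm.

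The conflict with intention to treat is also arguable, since analysing available values by assigned arm is often reported under that label. Finally, a mixed model does not settle deaths: it assumes that observed values explain the loss, and it implicitly extends trajectories past death.

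**Conclusion.** The point holds as one of efficiency and prespecification. The named infant tests use a single time point although four are collected, and the Statistical Plan offers competing methods whose choice could turn on observed loss. The 79% figure assumes 20 pairs and a true loss equal to the 20% allowance. In the simulations the mixed model's estimate had an SD of 0.35 to 0.48, against 0.48 to 0.55 for the t test. That gain rests on the assumed correlations and is partly due to baseline.

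Survivor bias is not demonstrated. Its size is unknown, and under the assumed value-dependent loss it is small against the sampling error. The missing rule for deaths is a real gap, but it calls for a clear statement rather than a conclusion that the infant results would be invalid. The primary milk analysis is not affected. The change should be made because it is cheap and these tests carry the infant aims.

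**What to change.** In the Statistical Plan:

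1. Replace the three t tests with one prespecified linear mixed model per outcome, used whatever the loss. Include all scheduled infant samples (baseline, weeks 2, 4 and 8) from every infant in a randomised pair. The test is the week-8 between-arm contrast, with small-sample degrees of freedom such as Kenward-Roger.
2. State that 0.05 for DHA and 0.025 for each cytokine apply to these three outcomes in place of the general Bonferroni sentence.
3. State whether a sample in the week 8 or discharge column that was taken before week 8 is modelled at the infant's actual age.
4. Keep all samples taken before a death, and report deaths and other losses before week 8 by arm.
5. Optionally add a supportive rank analysis of the cytokines with deaths ranked worst. Worst is high for TNF-alpha; the direction for IL-10 must be stated.

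The cost is SAP wording and modest programming, with no new samples, visits or participants. The downsides are the model's missing-data assumption and, for the rank analysis, the mixing of survival with cytokine level, which is why it should remain supportive.

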Study Design: Breast milk providers for enterally-fed preterm infants <29 weeks gestational age will be randomized to receive daily oral supplementation with DHA at 200mg or 1000mg. Based on our previous study with a placebo, it was apparent that even motivated mothers had a paucity of DHA in the diet and in their prenatal supplement therefore we felt it important to randomize to at least the baseline 200mg per day and then added the other dose as the target optimal dose for milk concentrations to achieve 0.8 mol weight percent. This concentration of DHA would provide intrauterine accretion when fed at 150ml/kg per day in the NICU. DHA concentration will be analyzed by gas chromatography in milk and infant cell membranes. Milk and infant plasma cytokine levels and cytokine production capacity will be measured. All samples will be obtained at baseline (within first week of life), weeks 2, 4, and 8. Inflammatory complications (BPD, NEC, and ROP) will be tracked. Cytokine gene expression from RNA extracted from the Week 4 milk samples will also be examined. Stool samples will not only have fatty acids but also bacteria and yeast analyzed.

Significance: Our unique investigation of maternal supplementation to improve DHA delivery to preterm infants represents the first study of its kind.

Purpose

The objective of this project is to improve preterm infant intake of DHA that approximate the levels obtained by fetal accretion during the third trimester of pregnancy and determine if there are functional relationships to inflammation, growth, and development.

The following specific aims will test the hypotheses that:

Aim 1: Maternal DHA supplementation will improve plasma and milk DHA concentration in the mother and preterm infant

Aim 2: Higher intakes of dietary DHA will decrease expression of pro-inflammatory cytokines and increase expression of anti-inflammatory cytokines in the plasma and milk samples of

breast feeding mother - infant dyads through the alteration of sRAGE signaling. This will result in an improved microbiome as evidence of bacteria and yeast in stool samples.

Background:

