Preterm infants miss the last trimester of nutrient accretion and may be deficient in essential molecules. These deficiencies may contribute to increased rates of infection and make these infants more vulnerable to disease [1]. Long chain omega-3 fatty acids, in particular docosahexaenoic acid (DHA), are preferentially transported across the placenta and provide components of membrane phospholipids that have been associated with improved markers of brain and retinal development [2-4]. Because the bulk of this transport occurs in the third trimester of pregnancy, premature infants do not benefit from this increase in DHA delivery. In adults, DHA can be synthesized from its precursor, linolenic acid - an essential fatty acid - through a series of elongase and desaturase enzyme activities that may be limited in the preterm infant [5]. The preterm infant may be particularly vulnerable to biosynthesis of DHA because of dietary protein limitations and steroid use thereby making a preformed dietary DHA source imperative – figure 1 ([name], Adv. Nutr, 2012).

Likewise, these DHA synthesizing enzymes are competitively shared by the omega-6 fatty acid series. Both the omega 6 and the omega 3 fatty acids, provide substrates for a host of pro- and anti-inflammatory lipid mediators. Omega 6 fatty acids are closely associated with the production of pro-inflammatory mediators and indirectly influence the production of tumor necrosis factor (TNF)- α . Conversely, omega-3 fatty acids are more closely linked to suppression of inflammation and production of anti-inflammatory or pro-resolution molecules. Specifically, DHA has been shown to suppress NFkB activation which results in decreased inflammatory responses and increased production of anti-inflammatory mediators such as interleukin (IL)-10 [6]. The maternal murine model supplemented with DHA promotes less inflammatory mediators in the lung of the pup and results in significantly better survival.[7] Deficits in nutrient sources of omega-3 long chain fatty acids, specifically DHA, may influence the infant's immune balance and contribute to development of disease [8, 9] [10] [11, 12].

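### A nearly free improvement, not an error: Holm testing of infant TNF-alpha and IL-10 keeps the 0.05 family-wise bound of the fixed 0.025 split and is never less powerful

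*Combined protocol and SAP*

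**What the plan says.** All of the testing rules are in the section headed Statistical Plan. The infant comparisons are set out as "We will use two sample t tests to compare infant blood DHA concentrations and TNF-alpha and IL-10 levels at 8 weeks". Infant blood DHA has its own level, 0.05. For the two cytokines the rule is that "the comparison of TNF-alpha and IL-10 levels will be performed at a significance level of 0.025 to adjust for the two outcomes". The section closes with "Secondary outcomes will use linear mixed models and Bonferroni correction". No step-down or other sequential procedure appears anywhere in the document.

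The scientific expectation is in Aim 2 under Purpose: "Higher intakes of dietary DHA will decrease expression of pro-inflammatory cytokines and increase expression of anti-inflammatory cytokines". Aim 2 names classes of cytokine, not TNF-alpha and IL-10. The Background supplies the link. It describes omega-6 fatty acids as "closely associated with the production of pro-inflammatory mediators and indirectly influence the production of tumor necrosis factor" (TNF-alpha), and it credits DHA with "increased production of anti-inflammatory mediators such as interleukin (IL)-10". Read together, these passages expect TNF-alpha to fall and IL-10 to rise.

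**The concern.** When a hypothesis expects both members of a two-test family to move, a fixed Bonferroni split loses power on the second test. Once one cytokine has passed 0.025, the only null hypothesis that can still be falsely rejected is the other one. It can then be tested at 0.05 without exceeding the family-wise bound, but the plan keeps it at 0.025.

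At stake is power in a small trial. The sample size of 8 per group was set for week-4 milk DHA, and the plan gives no power calculation for the cytokines. Any gain that needs no extra participants, samples or visits is worth considering.

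**Working it through.** **Inputs from the Statistical Plan.** Two-sample t tests; 0.025 for each of the two cytokines; 8 per group, which is the plan's target for evaluable week-4 data.

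**Inputs assumed.** A standardised difference d between arms, equal for both cytokines, from 0.8 to 2.0 SD, because the documents give no cytokine effect or SD. Also 8 per arm at week 8, because no week-8 number is stated. Outcomes are normal and, in the main calculation, independent.

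**Step 1: the plan's own figures.** 0.05 / 2 = 0.025, so the split is exact and valid. With two independent tests and no true effect, family-wise error is 1 - (1 - 0.025)² = 0.0494. The sample size also reproduces. For a two-fold difference (means 1 and 2) with SD 30% of each mean, the root-mean-square SD is √((0.3² + 0.6²)/2) = 0.474 and d = 1/0.474 = 2.11. A two-sided t test at 0.025 then needs 8 per group for 90% power (power 94%). This concerns milk DHA only and says nothing about cytokine power.

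**Step 2: power of one test.** With n = 8 per arm there are 14 degrees of freedom, and the noncentrality is d√(n/2) = 2d. Let p be the power at 0.025 and q the power at 0.05. At d = 1.5 the noncentrality is 3.0, p = 0.687 and q = 0.797.

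**Step 3: combine two independent outcomes.**
- At least one significant, either rule: 1 - (1 - p)²
- Both significant, fixed split: p²
- Both significant, Holm: 2pq - p²
- Each outcome, fixed split: p
- Each outcome, Holm: p + p(q - p)

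At d = 1.5, both significant is 0.687² = 0.471 under the fixed split and 2(0.687)(0.797) - 0.471 = 0.62 under Holm.

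| d (assumed) | p | q | Both: fixed 0.025 | Both: Holm | Each: fixed 0.025 | Each: Holm | At least one (either rule) |
|---|---|---|---|---|---|---|---|
| 0.8 | 0.217 | 0.320 | 4.7% | 9.2% | 21.7% | 23.9% | 38.7% |
| 1.0 | 0.338 | 0.461 | 11.4% | 19.7% | 33.8% | 37.9% | 56.1% |
| 1.25 | 0.514 | 0.643 | 26.4% | 39.7% | 51.4% | 58.0% | 76.3% |
| 1.5 | 0.687 | 0.797 | 47.1% | 62.2% | 68.7% | 76.2% | 90.2% |
| 2.0 | 0.917 | 0.960 | 84.1% | 92.0% | 91.7% | 95.7% | 99.3% |

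**Step 4: error rates.** These come from simulation, 200,000 trials per setting, 8 per arm.
- Neither cytokine affected: family-wise error is 4.9% at correlation 0 and 4.7% at ±0.5, identical under the two rules.
- One cytokine affected by 2 SD, the other not: the false-positive rate on the unaffected one is 2.5% under the fixed split and 4.6% to 4.8% under Holm. By formula at correlation 0, it is 0.025 + 0.917 x 0.025 = 0.048.

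**Step 5: sensitivity at 1.5 SD.**
- Correlation of size 0.5 whose sign agrees with the effect directions: both significant goes from about 53% to 66%.
- Correlation of size 0.5 running against the effect directions (for example, cytokines positively correlated within arm but moving opposite ways): 43% to 60%.
- Six per arm at week 8 (an assumption), independent outcomes: p = 0.512 and q = 0.650, so 26% to 40%.

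**The case against.** The strongest reply is that nothing in the plan is wrong, and that is correct. The split is prespecified, reasoned and valid, it would bias no conclusion, and the primary analysis of week-4 milk DHA is untouched.

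Four stronger readings are tempting, and the documents do not support them.

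- **That Aim 2 succeeds only if both cytokines change.** The plan states no such rule. If it did, no split would be needed: each test could be run at 0.05, with slightly more power for the joint claim than Holm (63.4% against 62.2% at 1.5 SD, independent outcomes). Aim 2 is also wider than these two tests. It covers plasma and milk of mothers and infants, and Study Procedures lists eight cytokines plus sRAGE.
- **That cytokine power improves generally.** The chance of at least one significant result is the same under both rules, 90.2% at 1.5 SD. Only the second rejection becomes easier.
- **That the fixed split buys nothing.** Both rules meet the same bound, but when one cytokine is affected and the other is not, the fixed split is stricter in practice (about 2.5% against nearly 5%).
- **That the same gain is established for all secondary outcomes.** The plan does not say how many outcomes are in that family, which they are, or whether TNF-alpha and IL-10 are among them. No gain can be computed, and exchanging one correction for another would leave the family just as undefined.

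It is also fair to object that at small effects the trial will seldom show both cytokines under either rule: 0.9% against 2.0% at 0.5 SD, and 4.7% against 9.2% at 0.8 SD. What survives these objections is that Holm rejects everything the fixed split rejects, sometimes more, within the same 0.05 bound whatever the correlation.

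**Conclusion.** The point stands as an efficiency gain that costs almost nothing, not as a flaw. That Holm keeps the bound and never rejects less needs no assumption about effects or correlation. The size of the gain does: for assumed equal effects of 0.8 to 2.0 SD, independent outcomes and 8 per arm at week 8, power to show both cytokines rises by about 4 to 15 percentage points and per-outcome power by about 2 to 8 points. Since the documents supply neither cytokine effects nor a week-8 number, these figures illustrate the gain and do not forecast it. The comparison of infant blood DHA, tested separately at 0.05, and the other measured cytokines are not affected.

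**What to change.** In the Statistical Plan, keep the level for infant blood DHA as it is and replace the cytokine part of that sentence with:

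> TNF-alpha and IL-10 will be tested by the Holm procedure at family-wise 0.05: the smaller p value against 0.025 and, if significant, the larger against 0.05.

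Make the change before the cytokine data are compared by arm. It needs no extra participants, samples or visits. The costs are simultaneous confidence intervals that are less simple than Bonferroni intervals (the plan specifies none) and the higher false-positive rate on an unaffected cytokine described above, still within the bound.

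Moving the remaining secondary outcomes from Bonferroni to Holm follows the same logic but is optional. If it is done, first list the outcomes in that family and say whether TNF-alpha and IL-10 belong to it, so that two overlapping Holm families are not created.
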